## 4.5.2 Missing Data for Efficacy and Safety Endpoints

### 4.5.2.1 Missing Data for Efficacy Endpoints

Missing visit data for each efficacy endpoint will be handled as described in Sections 3.2 and 4.3.1. For each continuous endpoint, change from baseline will be missing at visits with missing post-baseline values or where data were imputed to missing.

For the binary endpoints, subjects with missing efficacy data, early withdrawals, subjects who exceed the allowed dose of corticosteroid, who received new parenteral corticosteroids or more than one intra-articular corticosteroid injection within a 24 week period, or subjects who received rescue treatment will be imputed as non-responders and therefore treated as a failure (e.g. no DAS28(CRP) remission or no moderate/good EULAR response).

For subjects who exceed the allowed dose of corticosteroid, who received new parenteral corticosteroids or more than one intra-articular corticosteroid injection within 24 weeks or subjects who received rescue treatment, continuous efficacy endpoints will be set to missing.

- Missing efficacy data: visits with missing data (due to a missed visit or missing component of a composite endpoint) should be set to treatment failure.
- Early withdrawals (including subjects that are withdrawn at Week 36 due to lack of EULAR response): only visits following the early withdrawal visit should be set to treatment failure.
- Prednisone equivalent >10 mg/day: the visit after a period (time from previous visit up to the day before the current visit) of average daily corticosteroid use exceeding 10 mg/day prednisone and all following visits should be set to treatment failure (continuous endpoints will be set to missing).
- Parenteral corticosteroids: all visits after a subject received any new parenteral corticosteroids (e.g. intravenous and intra-muscular) should be set to treatment failure (continuous endpoints will be set to missing).
- Intra-articular corticosteroids: all visits after the second intra-articular corticosteroid injection within a 24 week period should be set to treatment failure (continuous endpoints will be set to missing).
- Rescue: subjects who rescue to 180 mg dose at Week 14 or 26 should be set to treatment failure at that visit and all subsequent visits (continuous endpoints will be set to missing).

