### DAS28(CRP) change from baseline

DAS28(CRP) scores and changes from baseline will be summarised for each visit. The mean change from baseline in DAS28(CRP) score and 95% CI will be plotted by randomised treatment group.

For change from baseline in DAS28(CRP) score, a mixed model repeated measures (MMRM) analysis will be conducted including all weeks up through Week 12. For the first interim the analysis will subset on those subjects with Week 12 DAS28(CRP) scores. The model will be fitted with fixed effects for randomised treatment group, visit, treatment by visit interaction and baseline DAS28(CRP), and visit within subject as a repeated effect. The covariance will initially be specified as unstructured covariance matrix. If SAS® gives a non-convergence warning, the

results will not be used – instead the warning will be stored and the spatial power law structure will be used in order to reduce the number of parameters to be estimated.

The point estimates and corresponding 95% CI for the treatment differences will be constructed using the residual error from the model; these estimates will be summarised and plotted for each randomised treatment group comparison over time.

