Markov-Chain-Monte-Carlo (MCMC) methods in SAS® will be used to derive the posterior distributions for each randomised treatment group and to also derive the distribution of the difference between each treatment group and the placebo group. From this difference distribution the posterior probability that the treatment difference between each active dose and placebo being  $> 1$  will be calculated.

Decision criteria for stopping the study after Interim Analysis 1 are specified in the DRC Statistical Guidance Document.

## DAS28 (CRP) remission rates at Week 24

The number and percentage of subjects achieving DAS28(CRP) remission ( $DAS28(CRP) < 2.6$ ) will be summarised for each randomised treatment group and visit. Fisher's exact test will be used to test for randomised treatment group differences at Week 24 in the proportion of subjects achieving remission for each GSK3196165 treatment group versus placebo.

## Predictive Probabilities at Week 24

The proportion of subjects with available DAS28(CRP) remission data at week 24 at the interim analysis will only be summarised using counts and proportions. This is because only a low number of subjects with week 24 data are expected at the week 12 interim analysis.

In addition, the predictive probability that the difference in DAS28(CRP) remission between each dose and placebo at the end of the study is  $> 15\%$  and  $> 25\%$ , given the results at the interim analysis and the prior information will be calculated using the procedure described below.

The following information will be available at the interim:

- $l_i$  = number of subjects that have reached week 24 in each randomised treatment group  $i$ ,  $i=0, \dots, 5$  ( $i=0$  being the placebo arm and  $i=1-5$  being the 5 treatment groups, with  $i=1$  being 22.5mg)
- $x_i$  = observed number of subjects in DAS28 remission at week 24 in each randomised treatment group  $i$ ,  $i=0, \dots, 5$  ( $i=0$  being the placebo arm and  $i=1-5$  being the 5 treatment groups, with  $i=1$  being 22.5mg)

Our prior Beta distribution on the remission rate in each randomised treatment group:  
 $\pi_i \sim \text{Beta}(\alpha_i^0, \beta_i^0)$

- Placebo:  $\alpha_0^0 = 9$ ,  $\beta_0^0 = 91$ , so the prior mean remission rate is 9%, and the 95th interval is (4%, 15%)
- Active group:  $\alpha_i^0 = 1$ ,  $\beta_i^0 = 1$ , equivalent to a uniform distribution (non informative). This will apply to all active groups ( $i=1$  to 5)

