Dose response analyses for DAS28(CRP) remission might be done as an ad-hoc analysis. MMRM analyses will be conducted similarly to interim analysis methods. Distributional assumptions underlying the model used for analysis will be examined by obtaining a normal probability plot of the residuals and a plot of the residuals versus the predicted values (i.e. checking the normality assumption and constant variance assumption of the model respectively) to gain confidence that the model assumptions are reasonable. If there are any departures from the distributional assumptions, alternative models may be explored using appropriate transformed data

For change from baseline in DAS28(CRP), if the dropout rate is  $\geq 10\%$  for the Week 24 or Week 52 analysis, further sensitivity analyses using multiple imputation as explained in section 4.5.2.3 may be conducted as ad-hoc analyses. In order to assess subgroup effects, additional analyses will be conducted with subgroup and subgroup interaction with treatment as covariates.

For DAS28(CRP) remission, subjects with missing data as defined in Section 3.2.1 will be imputed as non-responders as described in Section 4.5.2.1. Differences in remission rates between each active arm and placebo will be summarised at each visit through Week 52. 95% CI for the differences will be constructed using their asymptotic standard errors (asymptotic Wald confidence limits) without continuity correction.

Logistic regression models will have fixed effects for randomised treatment group and baseline value. The odds ratios, 95% CI and p-values for the comparison of each GSK3196165 treatment group versus placebo at key time points will be presented. Covariates age, gender, weight and disease duration ( $<2$  years,  $\geq 2$  years) will be considered in alignment with the results of the primary analysis model.

For ACR response, baseline values of TJC68 and SJC66 will be considered as fixed effects, as a baseline value of ACR response does not exist.

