For binary endpoints with repeated measures over time, Generalized Estimating Equations (GEE) methodology will be used to take correlation among subject-level responses over time into account. The model will include data from all assessment points from Week 1 to Week 62. Due to only few expected subjects with remission in some randomised treatment groups (especially placebo) only standard errors and resulting confidence intervals will be adjusted. To this end an independent working correlation structure will be assumed and standard errors will be calculated based on the empirical sandwich covariance estimate (default setting for PROC GENMOD in SAS) (Stokes, Davis, & Koch, 2012).

For the primary analysis of DAS28(CRP) remission at Week 24, the GEE model will include terms for randomised treatment group, baseline DAS28(CRP), visit and interaction terms for treatment group-by-visit and baseline-by-visit. A sensitivity analysis including covariates age, gender, weight and disease duration (<2 years,  $\geq 2$  years) will be considered by adding covariate terms to the repeated measures model one at a time along with the covariate-by-treatment group interaction term. If the interaction term is not significant at  $\alpha=0.10$  it will be removed from the model. Likewise, if the covariate term is not significant at  $\alpha=0.10$  it will be removed from the model. Other covariates will be tested in a similar manner.

Survival analyses (time to event analyses) will be conducted for the final analysis using Kaplan-Meier methods, comparing each GSK3196165 dose to placebo. Between-group differences will be analysed using the log-rank statistic. Median time to remission will be presented for each randomised treatment group. Kaplan-Meier plots of the time to remission will be presented. Subjects who withdraw from the study are censored at the time of withdrawal. All other subjects are censored at the end of the study.

In addition to summaries of the individual components of composite endpoints, numbers and percentages of subjects meeting the following criteria will be presented:

- TJC68  $\leq 1$
- SJC66  $\leq 1$
- CRP  $\leq 1\text{mg/dl}$
- PtGA  $\leq 10$
- SDAI  $\leq 3.3$

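### The primary Week 24 remission model has no finite odds ratio for any dose if no placebo subject is in remission, and the SAP names no fallback

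*SAP*

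**What the plan says.** SAP 4.9.2.2 defines the primary model: "For the primary analysis of DAS28(CRP) remission at Week 24, the GEE model will include terms for randomised treatment group, baseline DAS28(CRP), visit", with treatment-by-visit and baseline-by-visit interactions and an independence working correlation; "standard errors will be calculated based on the empirical sandwich covariance estimate". The reported results are set earlier in the same section: "The odds ratios, 95% CI and p-values for the comparison of each GSK3196165 treatment group versus placebo at key time points will be presented". Protocol 9.4.1 plans a logistic regression on treatment and baseline score.

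The SAP foresees sparse data. It says: "Due to only few expected subjects with remission in some randomised treatment groups (especially placebo) only standard errors and resulting confidence intervals will be adjusted". It gives no rule for an arm with no remitter at all.

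Three related provisions matter:

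- **Non-responder imputation (SAP 4.5.2.1):** "subjects who rescue to 180 mg dose at Week 14 or 26 should be set to treatment failure" at that visit and afterwards. A placebo subject escalated at Week 14 is therefore already a failure at Week 24.
- **Risk difference (SAP 4.9.2.2):** differences in remission rate are summarised, and "95% CI for the differences will be constructed using their asymptotic standard errors (asymptotic Wald confidence limits) without continuity correction". No p-value is attached.
- **Fisher's exact test:** for Week 24 remission it appears in SAP 4.9.2.1, under the interim analyses. It also underlies the sample size in SAP 4.13.1.

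By contrast, the SAP does say what to do if the MMRM fails to converge: "instead the warning will be stored and the spatial power law structure will be used in order to reduce the number of parameters".

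**The concern.** A sandwich variance changes the standard error around a point estimate. It cannot supply a point estimate that does not exist. The SAP's response to sparse placebo data therefore does not cover the extreme case of no placebo remitter at Week 24.

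All five dose comparisons share the placebo arm, so they fail together. The primary odds ratios, confidence intervals and p-values would all be lost, and the replacement would have to be chosen after the data were unblinded. The failure may also go unflagged, because software can stop iterating at a large finite value and report convergence.

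**Working it through.** **1. Why the model reduces to Week 24 alone.** Take visit as a class term, which is the ordinary reading although the SAP does not state the coding. For treatment t, visit v and baseline b, the model is

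logit p = α_v + β_(t,v) + γ_v·b.

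Under working independence the estimating equations are Σ x(y − p) = 0, summed over subjects and visits. Every parameter is specific to a visit, so the equations separate by visit. In a simulated six-arm dataset with two placebo remitters at Week 24, the GEE and the Week 24-only logistic fit gave the same five log odds ratios to five decimals (for example 1.86303 from both). Emptying some cells at Week 1 left the Week 24 estimates and standard errors unchanged.

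**2. What an empty placebo cell does.** The Week 24 equation for placebo is Σ(y − p) = 0 over placebo subjects. If every y is 0, it requires Σp = 0, which no finite α satisfies. So α goes to minus infinity, and the log odds ratio of any dose with a remitter goes to plus infinity. For a dose that also has none, it is undefined. Placebo remitters at other visits do not help.

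**3. How likely it is.** P(no placebo remitter) = (1 − p)^n. SAP 4.13 gives 35 as the minimum per arm. The two placebo rates in the SAP are 3% (4.13.1) and a Beta(9, 91) prior with mean 9% (4.9.2.1).

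| Placebo rate | n = 35 |
|---|---|
| 2% (assumed) | 0.98^35 = 49.3% |
| 3% (sizing) | 0.97^35 = 34.4% |
| 5% (assumed) | 0.95^35 = 16.6% |
| 9% (interim prior mean) | 0.91^35 = 3.7% |
| 15% (highest rate in SAP Table 11) | 0.85^35 = 0.3% |

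Averaged over the prior, the probability is B(9, 91 + n)/B(9, 91): 5.9% at n = 35, and 3.0% or 1.2% if placebo grew to an assumed 45 or 60.

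**4. What software returned.** Six-arm GEE fits with an empty placebo cell at Week 24 were run in Python statsmodels; SAS was not tested. All reported convergence. Log odds ratios were about 21 to 26. Standard errors were undefined or ran from 150 into the thousands. For 0/35 versus 11/35, p was 0.89 or more wherever it was defined, while Fisher's exact test gives p = 0.0004. These values are numerical artefacts. With one placebo remitter, the standard errors were an ordinary 1.0 to 1.6.

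**5. What a penalised fit gives.** In a two-arm, treatment-only comparison, Firth's estimate equals the odds ratio after adding 0.5 to each cell. For 0/35 versus 11/35 this is (11.5 × 35.5)/(24.5 × 0.5) = 408.25/12.25 = 33.3, which is finite. The penalised likelihood-ratio p-values are 0.048 for 0 versus 4, 0.022 for 0 versus 5 and 0.0099 for 0 versus 6.

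**6. The risk-difference interval.** For 0/35 versus 4/35 the difference is 11.4 points. The Wald standard error is √(0 + 0.1143 × 0.8857/35) = 0.0538, so the empty arm contributes no variance and the interval is 0.9% to 22.0%. The Newcombe interval is −0.6% to 26.0%. It includes zero although the Firth p is 0.048, so test and interval can disagree near the boundary.

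**7. The plan's own sizing figures.** Exact enumeration of Fisher's test at 3% versus 33% with 35 per arm gives 90.9% power, matching the stated figure of about 90%. The stated 17-point least significant difference matches Fisher at 0/35 versus 6/35 (6/35 = 17.1 points, p = 0.025; 5/35 gives p = 0.054). With 1/35 on placebo the smallest significant count is 8/35, a difference of 7/35 = 20.0 points.

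**The case against.** **The event may be unlikely.** The interim prior puts only 0.3% probability on a placebo rate of 3% or less, and SAP 3.1.4 expects placebo to exceed 35 if doses are dropped. This stands. A reader might take 34.4% as the probability, or as its upper limit. It is neither: it is the value at one of the SAP's two placebo rates, and 2% would give 49.3%.

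**Other results survive.** The dose-response model, the summarised risk differences and the interim stop and drop rules (SAP Table 4, which uses other quantities) do not depend on the odds ratio. This is a Phase II study without multiplicity adjustment. All of that is true and limits the damage, but the planned primary test would still be missing.

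**Fisher's test is already in the SAP.** SAP 4.9.2.1 names it for these Week 24 comparisons, so it is an obvious candidate. But it sits under the interim analyses, where the next paragraph limits Week 24 remission to counts and proportions, and nothing carries it into 4.9.2.2.

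**Two stronger readings are not supported.** A reader might infer that the model would produce false positives. A tiny p-value (1.6e-95) did arise for 0/35 versus 1/35, where Fisher gives 1.0, but only in a two-arm fit without baseline, which is not the planned model. In the six-arm fits every defined p-value for an empty placebo cell was far from significance. A reader might also infer that the 90% power is wrongly attributed to the GEE. It is not: SAP 4.13.1 names Fisher's exact test in that sentence. The 17-point sentence names no test, and an unpooled Wald half-width (16.6 points) also rounds to 17.

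**Conclusion.** The gap is real but conditional, and it should be fixed. If no placebo subject is in remission at Week 24 under non-responder imputation, all five primary odds ratios lack a finite estimate and the planned inference cannot be used. That follows from the model, whatever the software, given visit as a class term and working independence. The SAP has no fallback for this in 4.9.2.2, nor among the changes listed in 4.14.

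The size of the risk depends on which of the SAP's placebo rates is nearer the truth: about one in three at 3%, and about 4% to 6% under the interim prior, with 35 on placebo. The software behaviour was seen in statsmodels only. It shows that a convergence message cannot be relied on as the safeguard, not what PROC GENMOD would print.

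The power statement needs no correction. That the 17-point figure matches Fisher with an empty placebo arm is worth a note only.

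**What to change.** Add to SAP 4.9.2.2, before unblinding:

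- If placebo or the compared dose has no remitter at Week 24, the primary odds ratio, 95% confidence interval and p-value for that comparison come from Firth penalised logistic regression on Week 24 remission, with treatment and baseline DAS28(CRP), using the profile penalised-likelihood interval and test.
- The trigger is the Week 24 count under non-responder imputation, not a convergence message.
- In every other case the GEE stands as planned.
- In the triggered case the risk difference is given with a Newcombe interval, labelled descriptive, because it can disagree with the test near p = 0.05.

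The cost is a few lines of SAP text and a standard software option, with no change to patients or procedures. The downside is a slightly shrunken odds ratio when the rule applies. A simulation of the rule (six arms of 35, 5,000 runs per rate) gave type I error of 1.2% to 3.6% for common remission rates of 3% to 15%. It assumed a baseline SD of 1 and a log odds ratio of −0.7 per DAS28 point. Neither value is in the documents and only that one setting was run, so it is reassurance rather than proof.

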### **9.4.1. Primary Analyses**

The primary efficacy endpoint is the proportion of subjects achieving DAS28(CRP) remission at Week 24 of the 52-week double-blind treatment period in the ITT population using NRI. DAS28(CRP) remission is defined as a DAS28 score of <2.6 points. The DAS28(CRP) score is calculated using the following formula, where TJC = tender joint count, SJC = swollen joint count and PtGA = Patient's Global Assessment of Arthritis:

$$\text{DAS28(CRP)} = 0.56(\sqrt{\text{TJC28}}) + 0.28(\sqrt{\text{SJC28}}) + 0.36(\ln(\text{CRP} + 1)) + (0.014 * \text{PtGA}) + 0.96$$

Subjects with missing DAS28(CRP) scores at Week 24 will be considered as non-remitters. The proportion of subjects in DAS28(CRP) remission will be summarised using counts and proportions in remission and analyzed using a logistic regression analysis adjusted for treatment group and baseline DAS28(CRP) score and will be used to test the treatment comparison of each GSK3196165 dose group versus placebo. For each treatment comparison, an estimate of the odds ratio of achieving remission and the corresponding p-value and 95% confidence interval will be summarised.

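### The covariate sensitivity analysis of Week 24 remission keeps covariates and treatment interactions by p<0.10, so the adjusted model is partly chosen by chance

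*SAP*

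**What the plan says.** **Primary model.** Protocol 9.4.1 specifies a "logistic regression analysis adjusted for treatment group and baseline DAS28(CRP) score". SAP 4.9.2.2 turns this into a repeated-measures analysis in which "the GEE model will include terms for randomised treatment group, baseline DAS28(CRP), visit and interaction terms for treatment group-by-visit and baseline-by-visit". No term in either version is chosen from the data.

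**Sensitivity analysis.** The same SAP paragraph then introduces "A sensitivity analysis including covariates age, gender, weight and disease duration", which is to be considered "by adding covariate terms to the repeated measures model one at a time along with the covariate-by-treatment group interaction term". Two deletion rules follow. One begins "If the interaction term is not significant at" and the other "if the covariate term is not significant at"; in both the level is 0.10 and the term that fails is removed. The paragraph ends: "Other covariates will be tested in a similar manner".

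**Other models in SAP 4.9.2.2.** Logistic models have treatment and the baseline value as their default terms. The four covariates "will be considered in alignment with the results of the primary analysis model". The dose-response paragraph fits its main model without covariates, but allows covariates from the Week 24 remission analysis into a sensitivity model. SAP 4.9.1.3 lists candidate covariates for consideration and gives no selection rule of its own.

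**The concern.** A sensitivity analysis should show whether the primary conclusion survives a stated change of model. Here the changed model is unknown until the data have been tested, which has three consequences.

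- The covariate set is partly random, and the SAP describes no allowance for the selection in the standard errors or intervals.
- SAP 4.9.2.2 promises one odds ratio, interval and p-value for each dose against placebo. If a covariate-by-treatment term stays in, the treatment coefficient is the dose effect at one covariate value. It then answers a different question from the primary analysis. The SAP does not say which odds ratio would be reported.
- The procedure is not reproducible as written. It does not say whether retained terms accumulate, in what order covariates are tried, or which further covariates may be tried.

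The selected set may also reach the secondary binary endpoints, depending on how the alignment sentence for the logistic models is read.

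**Working it through.** **Inputs.** Retention level 0.10 and four candidates (SAP 4.9.2.2); 35 per arm, 33% active and 3% placebo remission, Fisher's exact test at two-sided 0.05 (SAP 4.13.1); alternative placebo rate 9% (prior mean in SAP 4.9.2.1).

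**The plan's own figure.** The documents give no figure for the selection rule, so only the design inputs can be checked. Summing Bin(x; 35, 0.03) × Bin(y; 35, 0.33) over all pairs with Fisher p ≤ 0.05 gives power of 90.9%, against about 90% stated. The inputs hold.

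**Chance of keeping a null term.** With k independent tests of exact size 0.10, the chance is 1 - (1 - 0.10)^k.

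- Four interactions (or four main effects): 1 - 0.9^4 = 1 - 0.6561 = 34.4%.
- All eight tests: 1 - 0.9^8 = 57.0%.

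**Placebo remitters at Week 24.**

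- At 3%: 35 × 0.03 = 1.05 expected; P(none) = 0.97^35 = 34%; P(none or one) = 72%.
- At 9%: 35 × 0.09 = 3.15 expected; P(none) = 4%; P(none or one) = 16%.

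For a two-level covariate with share q in one level, the chance that at least one placebo cell has no remitter is 1 - [1 - (1-p)^(35q)] × [1 - (1-p)^(35(1-q))].

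| Placebo rate | 40/60 split | 20/80 split |
|---|---|---|
| 3% | 84% | 89% |
| 9% | 37% | 55% |

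The 40/60 split follows the early-RA recruitment ceiling in SAP 3.1.1; the 20/80 split is an assumption. These are single-visit figures. The planned GEE pools Week 1 to Week 62, so its event base is larger.

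**Illustrative simulation.** Settings: 1,000 trials per setting, six arms of 35, active remission 33%, four covariates with no true effect (two continuous, two binary at 80% and 40%), a Week 24 logistic model, and likelihood-ratio tests with all five dose terms of an interaction tested jointly.

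| Placebo rate | Any main effect kept | Any interaction kept | Either |
|---|---|---|---|
| 3% | 32.5% | 43.4% | 62.2% |
| 9% | 36.0% | 44.0% | 64.8% |
| 15% | 35.5% | 42.5% | 62.8% |

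The interaction figures exceed 34% because each single test kept a null interaction in about 12% to 16% of trials rather than 10%. When at least one null main effect was kept and placebo had a remitter, dose odds ratios changed by a median factor of 1.03 to 1.05. The central 95% of changes ran from about 0.85 to 1.34 across settings. The effect of a kept interaction on the reported odds ratio was not simulated.

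**The case against.** The strongest reply is that little depends on this analysis.

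- **The primary result is untouched.** A reader might infer that the primary Week 24 odds ratios depend on the selection. The documents do not support that: the primary model is fully listed, and the 0.10 rule appears only in a sensitivity analysis that is itself only to be considered.
- **Carry-over is not mandated.** A reader might also infer that the selected terms are carried into all the secondary logistic models. The SAP says the covariates "will be considered in alignment with the results of the primary analysis model", and that model contains none of the four. The sentence could mean simply keeping the secondary models consistent with the primary. It mentions covariates, not interactions. Against this, the 0.10 screen is the only rule in the SAP that produces a result to align with, so carry-over is the more likely reading, though not a stated rule.
- **The list may be less open than it looks.** The closing sentence on other covariates could mean only the rest of the four. The SAP does not say.
- **The shifts are small.** A median factor of 1.03 to 1.05 is slight beside a design odds ratio of (0.33/0.67)/(0.03/0.97), about 16. This stands for main effects; it does not cover a retained interaction.
- **Any added covariate changes a logistic odds ratio.** This is true of the proposed model as well. The difference is that its target is fixed before the data are seen and gives one odds ratio per dose.
- **No decision rests on it.** Interim stopping and arm dropping use dose-response estimates and predictive probabilities, and the main dose-response model has no covariates. This stands and limits the importance of the point.

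**Conclusion.** The point holds as a minor one. The p<0.10 rule makes the covariate sensitivity analysis of Week 24 remission data-driven. If an interaction is kept, the analysis no longer checks the primary result. The chance of keeping at least one of four null interactions is about 34%, assuming independent tests of nominal size. The single-visit simulation gave 43% to 44%. Neither is the rate for the planned pooled-visit GEE with sandwich standard errors, which may differ. Sparse placebo remission makes the interaction tests fragile (about 1 remitter of 35 at Week 24 at 3%, about 3 at 9%), though less so once visits are pooled.

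The primary model, sample size and power are unaffected. Spread to the secondary logistic models is a plausible reading of an unclear sentence. Use in dose response is allowed only as a sensitivity analysis.

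**What to change.** In SAP 4.9.2.2:

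1. Replace the 0.10 rule with one prespecified sensitivity model: the primary GEE terms plus age, gender, weight and disease duration as main effects, all kept whatever their p-values. Delete the sentence on other covariates, or name them.
2. Report each covariate-by-treatment interaction separately as a subgroup check. The plan already has subgroup summaries by disease duration and, where numbers allow, gender, and subgroup-by-treatment analyses in its paragraph on DAS28(CRP) change, so this extends existing work.
3. Replace the alignment sentence with a fixed set for the secondary logistic models: treatment and baseline value, with the same four main effects only in a sensitivity analysis. Keep the existing provision for ACR response, which has no baseline value.
4. Point the dose-response sensitivity analysis to the same fixed set.

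The cost is SAP wording and less programming than a selection procedure. With no selection tests, the chance of keeping a null term through selection falls to zero. The downside is four extra parameters (one per covariate, with age and weight linear) in a sensitivity model with few placebo events, so that model may be imprecise and should be reported as such.
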